2.3.2. Potential Risks

ALVR105 primarily targets cells infected with AdV, BKV (and/or JCV), CMV, EBV, and/or HHV-6. The main risks of administration are inflammation at sites of existing disease or GVHD due to cross-reactivity with the recipient's HLA antigens. Adverse events attributable to virus-specific T cell administration may potentially occur in a small percentage of the treated population. These can include both hematologic and non-hematologic effects, as reported in the CHARMs

study.

Studies of donor-derived virus-specific T cells suggest that virus-specific T cells do not persist in patients who receive methylprednisolone in doses ≥ 1 mg/kg/day. Therefore, if patients develop severe inflammatory reactions thought to be attributable to ALVR105, a therapeutic option is to administer methylprednisolone (1 to 2 mg/kg/day). In patients who develop skin rash or skin GVHD, excellent responses have been noted with the administration of topical steroids.

As with other biological therapies delivered by IV infusion, the side effects of ALVR105 infusion include allergic reactions (anaphylaxis), decreased oxygenation, nausea/vomiting, arrhythmia, and hypotension.

A detailed breakdown of the timepoints and blood volumes to be collected during the course of this study is provided in the Laboratory Manual.

In order to minimize the volume of blood collected during the study trial, the blood volume of individual samples has been reduced to the maximum extent feasible wherever possible. This has been performed in a manner that is expected to maintain the scientific integrity of the study and related data, while minimizing the risks to the patients.

In order to minimize the volume of blood collected during the study, especially for pediatric patients, the blood volume of individual samples has been reduced to the maximum extent feasible wherever possible. For pediatric patients < 12 years of age, collection of blood samples for the evaluation of viral load for all six viruses (AdV, BKV, CMV, EBV, and/or HHV-6, and JCV) is limited to every other week and blood volume is sufficient for testing only AdV viremia in the other weeks. Pediatric patients also do not participate in pre-screening blood samples. This reduction in volume of blood collection has been done in a manner that is expected to maintain the scientific integrity of the study while minimizing the risks to patients. For maximum blood draw volumes, see the Laboratory Manual.

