1 INTRODUCTION

The purpose of this Statistical Analysis Plan (SAP) is to provide a description of the statistical methods to be implemented for the analysis of data from the Phase 2 open label (OL) cohort of Protocol P-105-202. All the patients in the Phase 2 OL were enrolled, treated, and followed under Protocol Amendment 2 dated 7 April 2021. Data were collected under Protocol Amendment 2 Schedule of Activities ([Appendix 2](#)). The analysis will be based on Protocol Amendment 4 dated 19 October 2021. In addition, the clinically significant infections or episodes of end-organ disease were determined by the clinical investigators in Phase 2. [REDACTED]

The SAP will be finalized prior to Phase 2 database lock. Any deviations from the SAP after database lock will be documented in the final Clinical Study Report (CSR) for the Phase 2 OL cohort. [REDACTED].

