3.4.2 Secondary Efficacy Endpoints

The key secondary endpoint is the number of clinically significant infections or episodes of end-organ disease per patient due to AdV, BKV, CMV, EBV, HHV-6, or JCV through Week 26. The definition of clinically significant infections or episodes is the same as for the primary endpoint. The summary statistics will be provided by each individual virus at Week 14 and 26, respectively.

Similar analysis will be performed for the clinically significant infections or episodes of end-organ disease per patient due to AdV, BKV, CMV, EBV, HHV-6 or JCV, from each individual virus through Week 14 and Week 26 (i.e., 6 endpoints each at Week 14 and Week 26).

The mean viral load for each AdV, BKV, CMV, EBV, HHV-6, and JCV virus, obtained as AUC/number of days at Week 14 and Week 26, will be summarized by descriptive statistics in the original and log10 scales. For each virus, the viral load and change from baseline over time will also be summarized in the original and log10 scales.

By-patient listings will be provided for the clinically significant infections or episodes of end-organ disease per patient due to AdV, BKV, CMV, EBV, HHV-6, or JCV.

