3.4.3 Exploratory Efficacy Endpoints

The exploratory efficacy endpoints are listed in Section 2.3.3.

The observed and change from baseline in QoL assessments will be summarized through Week 26. Listings will be provided for the QoL assessments.

Since most of the patients are undetectable, the number and percentage of patients with detectable viremia (i.e., \geq LLOQ) will be summarized at Week 14 as well as by visit and at any visit.

By-patient listing will be provided for AdV, BKV, CMV, EBV, HHV-6, and/or JCV viremia and QoL measures.

Subgroup analyses may be conducted for the efficacy endpoints by type (class I or II), the number of HLA matches, and letermovir treatment at Baseline.

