^l Viral loads of BKV, AdV, CMV, JCV, and HHV-6 in plasma and of EBV in PCMBs will be measured weekly for adult patients and pediatric patients ≥ 12 years old after allogeneic HCT conditioning during pre-screening period and screening period until treatment assignment, if possible. Pediatric patients < 12 years old will have only one blood draw during the Screening visit and will not have weekly blood draws during the screening period. Viral load testing should NOT be done on day of HCT during pre-screening. The results of the repeat analyses from the screening period must be available at the time of treatment assignment, unless the timing of the Screening Visit is 1 week or less before treatment administration. Results of central laboratory testing for viral load will be used for the purpose of determining eligibility/inclusion.

^m Adult patients and pediatric patients ≥ 12 years old only.

Table 6. Schedule of Activities: Treatment - Period 1 for Patients \geq 12 Years of Age (Week 1 to 14, All Cohorts)

Time Period	Treatment Assignment	Study Drug Administration Day	Treatment Period													
			Wk 1	Wk 2	Wk 3	Wk 4	Wk 5	Wk 6	Wk 7	Wk 8	Wk 9	Wk 10	Wk 11	Wk 12	Wk 13	Wk 14
Study Day		1 ^a	8	14	21	28	35	42	49	56	63	70	77	84	91	98
Visit Window (Days)		NA ^b	± 3	± 5	± 3	± 5	± 3	± 5	± 3	± 5	± 3	± 5	± 3	± 5	± 3	± 3
Study Procedures																
Review of I/E criteria		X														
Prior & concomitant medications as well as conditioning regimen for HCT		X		X		X		X		X		X		X		X
Adverse events ^c		X		X		X		X		X		X		X		X
Physical examination ^d		X		X		X		X		X		X		X		X
Weight		X				X				X				X		X
Vital signs ^e		X		X		X		X		X		X		X		X
12-lead ECG ^f		X		X		X		X		X		X		X		X
Clinical labs ^g		X		X		X		X		X		X		X		X
Pregnancy test ^h		X		X		X		X		X		X		X		
BKV, AdV, CMV, JCV, and HHV-6 viral load ⁱ		X	X	X	X	X	X	X	X	X	X	X	X	X	X	X
EBV PCMBs ^j		X	X	X	X	X	X	X	X	X	X	X	X	X	X	X
Treatment Assignment ^j	X															

Time Period	Treatment Assignment	Study Drug Administration Day	Treatment Period													
			Wk 1	Wk 2	Wk 3	Wk 4	Wk 5	Wk 6	Wk 7	Wk 8	Wk 9	Wk 10	Wk 11	Wk 12	Wk 13	Wk 14
Study Day		1 ^a	8	14	21	28	35	42	49	56	63	70	77	84	91	98
Visit Window (Days)		NA ^b	±3	±5	±3	±5	±3	±5	±3	±5	±3	±5	±3	±5	±3	±3
Study Procedures																
Virus-Specific T Cell Assessment ^k		X				X		X			X		X			X
Study treatment administration ^l		X		X		X		X		X		X		X		
Post infusion monitoring ^m		X		X		X		X		X		X		X		
Infection assessment ⁿ		X	X	X	X	X	X	X	X	X	X	X	X	X	X	X

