sample for AdV, BKV, CMV, HHV-6, and JCV and a PBMC sample for EBV for PCR testing at the central laboratory should be collected. Patients who develop viral infections will continue to be followed in the study and complete all remaining visits through Week 26.

◦ Assessment of quality of life (using FACT-BMT, EQ-5D-5L, EQ-5D-Y, EQ-5D-Y Proxy Version 1questionnaires, as age-appropriate) should be completed prior to any study procedures at this visit.

Table 7. Schedule of Activities: Treatment - Period 1 for Patients <12 Years of Age (Week 1 to 14, All Cohorts)

Time Period	Treatment Assignment	Study Drug Administration Day	Treatment Period													
			Wk 1	Wk 2	Wk 3	Wk 4	Wk 5	Wk 6	Wk 7	Wk 8	Wk 9	Wk 10	Wk 11	Wk 12	Wk 13	Wk 14
Study Day		1 ^a	8	14	21	28	35	42	49	56	63	70	77	84	91	98
Visit Window (Days)		NA ^b	±3	±5	±3	±5	±3	±5	±3	±5	±3	±5	±3	±5	±3	±3
Study Procedures																
Review of I/E criteria		X														
Prior & concomitant medications as well as conditioning regimen for HCT		X		X		X		X		X		X		X		X
Adverse events ^c		X		X		X		X		X		X		X		X
Physical examination ^d		X		X		X		X		X		X		X		X
Weight		X			X				X				X		X	
Vital signs ^e		X		X		X		X		X		X		X		X
12-lead ECG ^f		X		X		X		X		X		X		X		X
Clinical labs ^g		X		X		X		X		X		X		X		X
Pregnancy test ^h		X		X		X		X		X		X		X		
BKV, CMV, JCV, and HHV-6 viral load ⁱ		X		X		X		X		X		X		X	X	X
EBV PBMCs ^j		X		X		X		X		X		X		X	X	X
AdV viral load		X	X	X	X	X	X	X	X	X	X	X	X	X	X	X
Treatment Assignment ^j	X															
Virus- Specific T Cell Assessment ^k		X				X		X			X			X		X
Study treatment administration ^l		X		X		X		X		X		X		X		

Time Period	Treatment Assignment	Study Drug Administration Day	Treatment Period													
			Wk 1	Wk 2	Wk 3	Wk 4	Wk 5	Wk 6	Wk 7	Wk 8	Wk 9	Wk 10	Wk 11	Wk 12	Wk 13	Wk 14
Study Day		1 ^a	8	14	21	28	35	42	49	56	63	70	77	84	91	98
Visit Window (Days)		NA ^b	±3	±5	±3	±5	±3	±5	±3	±5	±3	±5	±3	±5	±3	±3
Study Procedures																
Post infusion monitoring ^m		X		X		X		X		X		X		X		
Infection assessment ⁿ		X	X	X	X	X	X	X	X	X	X	X	X	X	X	X
Quality of Life (FACT- BMT, EQ-5D-5L, EQ-5D-Y, EQ-5D-Y Proxy Version 1) ^o		X					X			X				X		X

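### Under-12s have fewer scheduled samples for five of the six viruses, so the any-visit viremia rate and the odd-week rows for Weeks 1 to 11 depend partly on the sampling schedule

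*SAP*

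**What the plan says.** SAP section 1 fixes which schedule produced the data: "Data were collected under Protocol Amendment 2 Schedule of Activities", reproduced in SAP Appendix 2.

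- **Age 12 and over (SAP Table 6).** The row "BKV, AdV, CMV, JCV, and HHV-6 viral load" and the separate EBV row are marked on Day 1 and every week to Week 14.
- **Under 12 (SAP Table 7).** The row "BKV, CMV, JCV, and HHV-6 viral load" and the EBV row are marked on Day 1 and Weeks 2, 4, 6, 8, 10, 12, 13 and 14. A separate row, "AdV viral load", is marked every week.

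Protocol 2.3.2 shows that the difference is deliberate. To spare blood in young children, six-virus sampling is "limited to every other week and blood volume is sufficient for testing only AdV viremia in the other weeks".

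The analysis does not carry this distinction forward. Under SAP 3.4.3, the count and percentage with detectable viremia "will be summarized at Week 14 as well as by visit and at any visit". SAP 3.4.2 adds, for each virus, that "the viral load and change from baseline over time will also be summarized in the original and log10 scales". Both use the Safety Population (SAP 3.2.2) and one weekly set of viral-load windows for all ages (SAP Appendix 1, Table 2), with data taken as observed (SAP 3.1.5). The optional efficacy subgroups in SAP 3.4.3 are HLA type, number of HLA matches and baseline letermovir; age is not among them.

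**The concern.** An any-visit percentage depends on how often patients are looked at. Pooling patients who have 14 looks with patients who have 8 lets the result vary with the age mix as well as with viremia.

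The by-visit rows have a related problem. In the six odd weeks up to Week 11, children have no scheduled sample for five viruses. If the denominator is the whole Safety Population, children count as not detectable without having been tested, and those rows drop. If the denominator is patients tested, the rows switch between patients aged 12 and over (odd weeks) and all ages (even weeks), so they can alternate whenever prevalence differs by age. The same change of population applies to the viral-load summaries over time in SAP 3.4.2.

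What is at stake is how descriptive tables are read. No test or decision rule rests on these rows.

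**Working it through.** The plan states no rate or precision for these summaries, so there is no figure to reproduce. The counts below come from the documents; every rate is an assumption.

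**Inputs from the documents**
- Post-baseline sampling days to Week 14, age 12 and over: 8, 14, 21, 28, 35, 42, 49, 56, 63, 70, 77, 84, 91, 98 (SAP Table 6).
- The same for five viruses under 12: 14, 28, 42, 56, 70, 84, 91, 98 (SAP Table 7).
- Eligibility starts at age 1 (Protocol 5.1). The cohort is 25 to 35 patients (SAP 2.2.3). The number under 12 is not given.

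**Assumptions**
- A share f = 20% of patients is under 12 (range 10% to 40%).
- 30% of patients have one episode of L days, with onset uniform over Days 1 to 98 (a span of 97 days).

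**1. Counts.** Post-baseline samples number 14 against 8 (15 against 9 with Day 1). AdV has 14 in both groups. The days without a scheduled sample under 12 are 8, 21, 35, 49, 63 and 77, which are Weeks 1, 3, 5, 7, 9 and 11.

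**2. Chance that one episode meets a sampling day.** This is the sum over sampling days of min(L, gap), divided by 97, where gap is the number of days since the previous sampling day (since Day 1 for the first).
- Age 12 and over: gaps are 7, 6, then twelve of 7. For L = 7: (7 + 6 + 84)/97 = 100%.
- Under 12: gaps are 13, five of 14, then 7 and 7.
  - L = 7: 8 × 7/97 = 56/97 = 58%.
  - L = 10: (6 × 10 + 2 × 7)/97 = 74/97 = 76%.
  - L = 14: (13 + 70 + 14)/97 = 100%.

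**3. Any-visit rate with 7-day episodes.**
- Under 12: 0.30 × 0.577 = 17.3%.
- Overall: 0.30 × [(1 − f) + 0.577f], which is 27.5% at f = 20%, 28.7% at 10% and 24.9% at 40%. Weekly sampling of everyone would give 30%.
- At f = 20% the shortfall is 2.5 points, or 0.025 × 25 = 0.6 to 0.025 × 35 = 0.9 of a patient.

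**4. Any-visit rate under a different model.** With independent samples, each positive with probability p, the chance of at least one positive is 1 − (1 − p)^k for k samples.

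| p | 14 samples | 8 samples |
|---|---|---|
| 0.02 | 24.6% | 14.9% |
| 0.05 | 51.2% | 33.7% |
| 0.10 | 77.1% | 57.0% |

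**5. Odd-week rows at f = 20%.**
- Prevalence 20% at every age, Safety Population as denominator: 20% × 0.8 = 16% in odd weeks, 20% in even weeks.
- Same prevalence, patients tested as denominator: 20% in both.
- Prevalence 20% at 12 and over and 35% under 12, patients tested: 0.8 × 20% + 0.2 × 35% = 23% in even weeks, 20% in odd weeks.

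**6. After restriction to common visits.** Both groups have 8 scheduled post-baseline samples up to Week 14, so the scheduled difference is zero.

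**The case against.** The listed endpoint in SAP 2.3.3 is undetectable viremia at Week 14, when every age is sampled. The by-visit and any-visit figures are additions in a single-arm cohort of 25 to 35 patients, and the primary and key secondary endpoints are not computed from them. That stands, and it limits the weight of the point.

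The documents also soften the gap. Infection assessments are weekly in children, and starting antiviral treatment calls for a central sample covering all six viruses (Protocol 8.3.2). Unscheduled samples enter the analysis windows (SAP 3.1.2). Even-week visits may shift by 5 days: a Week 2 visit (Day 14) on Days 9 to 11 falls in the Week 1 window, which runs to Day 11. What is missed is therefore mainly short, untreated viremia. Viral-load summaries show the count of available values, so a smaller odd-week count would be visible, and by-patient listings are planned. All this reduces the problem, but it leaves the any-visit percentage without an age split or stated denominator.

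The sizes rest on assumed inputs. That is also right: the child share, episode length and age-specific prevalence are not given.

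Three stronger readings are tempting, and the documents do not support them:
- **Capture of 50% for a 7-day and 71% for a 10-day episode.** This treats paediatric sampling as fortnightly throughout. SAP Table 7 marks Weeks 12, 13 and 14, which gives 58% and 76%.
- **AdV made to look more frequent in the group most at risk from it.** The SAP summarises each virus separately and plans no contrast between viruses within children. Protocol 2.2 gives an AdV incidence for children but no adult figure to compare with it.
- **By-visit rates necessarily move with the schedule.** With patients tested as denominator and equal prevalence across ages, they do not.

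**Conclusion.** The point holds as a minor one. For BKV, CMV, EBV, HHV-6 and JCV, the any-visit percentage can read low in children, and the rows for Weeks 1, 3, 5, 7, 9 and 11 have no scheduled samples from them. The Week 14 summary, the even weeks, Week 13 and AdV are not affected.

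The sample counts are firm. That ages are pooled is inferred from the single Safety Population, the common windows and the absence of an age subgroup; the SAP does not say so in words. The size is conditional. In the single-episode illustration the overall any-visit rate loses about 1 to 5 points for a child share of 10% to 40%. The loss is nil for episodes of 14 days or more, and there is no effect at all if no child under 12 was dosed.

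**What to change.** In SAP 3.4.2 and 3.4.3, for the five viruses:

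1. Use the number of patients tested at each visit as the denominator of by-visit percentages, and show it.
2. Label the rows for Weeks 1, 3, 5, 7, 9 and 11 as patients aged 12 and over. Item 1 alone does not make odd and even weeks the same population.
3. Report the any-visit percentage by age group (under 12; 12 and over).
4. Give the all-age any-visit figure on the visits common to both schedules: Day 1, Weeks 2, 4, 6, 8, 10, 12, 13 and 14, then follow-up. Keep the full weekly result as a second row.

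The cost is SAP wording and table programming; no new data are needed. The common-visit figure sets aside 6 of the 14 post-baseline samples up to Week 14 in each older patient, which is why the weekly row should stay. The under-12 group may be very small: 5 to 7 patients at a 20% share of 25 to 35. Its percentage should therefore be shown with the counts.

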3.5 Safety Analyses

Safety data will be summarized based on the Safety Population. Categorical endpoints will be summarized using the number and percentage of patients within each category. Continuous endpoints will be summarized descriptively with summary statistics (number of non-missing observations, arithmetic mean, standard deviation, median, minimum, and maximum).

3.5.1 Adverse Events (AEs)

All AEs will be coded to system organ class and preferred term using MedDRA. Treatment emergent adverse events (TEAEs) are defined as an AE with onset or worsening on or after the first dose of study treatment through the end of study (i.e., Week 26).

An overall summary of AEs will be provided with the number and percentage of patients who experienced at least 1 AE or TEAE in the following categories:

- Any TEAEs
- Any TEAEs by severity
- Any treatment-related TEAEs
- Any AEs of special interest (AESIs)
- Any treatment-emergent AESI (TEAESIs)
- Any treatment-related TEEAESIs
- Any serious AEs (SAEs)
- Any treatment-emergent serious AEs (TESAEs)
- Any treatment-related TESAEs
- Any TEAEs leading to discontinuation of study treatment
- Any TEAEs leading to discontinuation of study
- Any AEs leading to death

The numbers and percentages of patients will also be presented by system organ class (SOC) and preferred term (PT) for each of the TEAE categories in the summary. Patients with multiple AEs will be counted only once per SOC and PT. The number and percentage of patients with TEAEs will be tabulated by PT and by the highest CTCAE Grade.

Listings will be presented specifically for any AEs, deaths, SAEs, and TEAEs leading to discontinuation of study treatment and study.

3.5.2 AEs of Special Interest

Adverse events of special interest (AESI) include infusion-related AEs, GVHD, and cytokine release syndrome (CRS). These AESIs will be reviewed by the DSMB as per the DSMB Charter. Criteria for acute and chronic GVHD and CRS can be found in Protocol Appendix 5 and 6, respectively. The number and percentage of patients who had the AESIs will be summarized:

- Severity and incidence of acute GVHD
- Severity and incidence of chronic GVHD
- Severity and incidence of CRS
- Severity and incidence of infusion-related AEs
- Severity and incidence of graft failure

Subgroup analyses may be conducted for the severity and incidence of acute GVHD by HLA type and the number of HLA matching.

